#### **1.2.2.2. Administration of the investigational ChAd3-EBO-Z vaccine**

Considering the risk of exposure to Ebola and the potential (based on animal data) for the investigational ChAd3-EBO-Z vaccine to afford at least partial protection, all children in the study will receive the investigational ChAd3 EBO-Z vaccine. The children in the Group EBO-Z/ MENACWY-TT will receive the investigational ChAd3-EBO-Z vaccine at Day 0 of the study, whereas the children in the Group MENACWY-TT/ EBO-Z will receive *Nimenrix* at Day 0 (as a control). At Month 6, the children in the Group MENACWY-TT/ EBO-Z will receive the investigational ChAd3-EBO-Z vaccine (provided that no safety concerns are raised. Refer to [Section 9.10](#) for more information on the IDMC) whereas the children in the Group EBO-Z/ MENACWY-TT will receive *Nimenrix*.

In case the geographic range of EBOV transmission expands to encompass any of the regions where this trial is conducted, earlier administration of the investigational ChAd3-EBO-Z vaccine to the children in the Group MENACWY-TT/ EBO-Z will be considered in that region.

#### **1.2.2.3. Control vaccine**

GSK Biologicals' meningococcal serogroups A, C, W-135, Y tetanus toxoid conjugate (MenACWY-TT) vaccine (*Nimenrix*) will be used as control.

*Nimenrix* is indicated for the active immunisation against invasive meningococcal diseases caused by *Neisseria meningitidis* (meningococcus) serogroups A, C, W-135 and Y. Invasive meningococcal disease, including meningitis and meningococcal septicaemia, often follows invasive infection by *Neisseria meningitidis* and is a major cause of death and morbidity throughout the world. *Neisseria meningitidis* serogroups A, B, C, W-135

and Y are the most common causes of invasive meningococcal disease worldwide: serogroup A is most common in Africa and Asia, while serogroups B and C account for more than 90% of the cases in Europe and Latin America [Anderson, 1998; Connolly, 1999; Harrison, 2009; Peltola, 1998]. *Nimenrix* is licensed in 50 countries (first approval in April 2012) and is currently available in at least 23 countries.

Using *Nimenrix* as a control vaccine in this study will provide a theoretical benefit to the children in the study and adequately support safety comparison.

#### **1.2.2.4. Stratification for age and staggered vaccination**

In order to ensure equal distribution of the population, enrolment will be stratified by age so that equal number of children are enrolled in each age stratum (1 to 5 years, 6 to 12 years and 13 to 17 years of age).

In order to ensure maximum safety for the subjects in this study, vaccination at Day 0 will be done in a staggered manner, starting with vaccination of the children in the oldest age stratum. For each age stratum, an IDMC will conduct a review of all available safety data once data is available up to at least 7 days after vaccination of at least 50 subject (25/ group) in that age stratum. The start of vaccination in the younger age stratum, possibly with a lower vaccine dose, depends on the outcome of this IDMC review. For more detailed information on the staggered design of the study and on the safety monitoring, refer to [Section 9.10](#).

#### **1.2.2.5. Human immunodeficiency virus testing**

There will be no routine testing for human immunodeficiency virus (HIV) in this trial. Tests will be performed when clinically indicated to guide subject management. Voluntary counselling and testing, highly active anti-retroviral therapy (HAART) and prevention of mother to child transmission (PMTCT) will be available at all study centres according to national policies.

### **1.3. Benefit : Risk assessment**

All subjects in the study will receive a single dose of the investigational ChAd3-EBO-Z vaccine (either at Day 0 or at Month 6 of the study) and a single dose of *Nimenrix* (at Day 0 or at Month 6 of the study).

For general information on the risks and benefits of the investigational ChAd3-EBO-Z vaccine and *Nimenrix*, please refer to the current Investigator Brochure (IB), Periodic Safety Report Information (PSRI) and to the approved summary of product characteristics (SmPC)/ Prescribing Information/ package insert, as applicable.

The following section outlines the risk assessment and mitigation strategy for this study protocol.

**1.3.1. Risk Assessment**

Important Potential/Identified Risk	Data/Rationale for Risk	Mitigation Strategy
Both study vaccines		
As with all injectable vaccines, allergic reactions to vaccination can occur.	Acute allergic reactions such as a rare case of anaphylactic event may occur with any vaccine administration. These are serious, but rare occurrences estimated in the range of 1 to 10 cases per million of vaccinations, depending on the vaccine studied [Rüggeberg, 2007]. No such event has been observed as of 14 November 2014 in the on-going Phase 1 trials with the investigational ChAd3-EBO-Z vaccine.	Warnings regarding allergic reactions. Anaphylaxis following vaccine administration is an exclusion criterion for study participation and a contraindication to vaccination. The onset of vaccine-related allergic symptoms is typically quite prompt. In order to treat subjects with a serious allergic reaction to vaccination, all subjects will need to remain under observation ( i.e. , visibly followed; no specific procedure) at the vaccination centre for at least 30 minutes after vaccination.
Syncope	Syncope (fainting) can occur following, or even before, any vaccination especially in adolescents as a psychogenic response to the injection needle (also outlined in the Nimenrix Reference Safety Information). This can be accompanied by several neurological signs such as transient visual disturbance, paraesthesia and tonic-clonic limb movements during recovery.	It is important that procedures are in place to avoid injury from faints. All subjects will need to remain under observation ( i.e. , visibly followed; no specific procedure) at the vaccination centre for at least 30 minutes after vaccination.
Nimenrix		
Extensive limb swelling	The active ingredients of Nimenrix are conjugated to a tetanus toxoid carrier protein and exaggerated local (Arthus-like) reactions are occasionally reported following receipt of a diphtheria- or tetanus-containing vaccine. These reactions present as extensive painful swelling, often from shoulder to elbow. They generally begin from 2 to 8 hours after vaccination and are reported most often in adults, particularly those who have received frequent doses of diphtheria or tetanus toxoid.	Subjects' parent(s)/ LAR(s) should report any untoward symptoms experienced by the child after receiving the vaccine immediately to the Investigator.

**ChAd3-EBO-Z** = investigational recombinant chimpanzee adenovirus type 3-vectored Ebola virus Zaire (EBOV) vaccine; **GSK** = GlaxoSmithKline

### 1.3.2. Benefit assessment

#### **Benefits linked to the investigational ChAd3-EBO-Z vaccine**

The subjects in this study may not directly benefit from vaccination with the investigational ChAd3-EBO-Z vaccine as the vaccine has not been assessed in subjects exposed to EVD yet and it is hence not known whether it is effective in protecting against EVD. Moreover, this study will be conducted in countries adjacent to the current Ebola outbreak zone and the subjects in this study possibly may never come in contact with EBOV.

An indirect benefit is that the information obtained in this study will aid the development of a vaccine against EVD.

#### **Benefits linked to *Nimenrix***

Meningococcal disease continues to be endemic in both industrialised regions (such as North America and Europe) and developing regions and is associated with high case fatality even where adequate medical services and antibiotics are available. However, a significant decline in the incidence of confirmed meningococcal disease has been observed in those countries that include meningococcal vaccination in their routine immunisation schedule. Overall, clinical trial data and post-marketing experience continue to demonstrate the substantial benefit and acceptable safety profile of *Nimenrix* vaccination.

#### **Other benefits**

***All subjects who provide informed consent for study participation will be tested for Malaria infection using an RDT procedure at the time of Screening. Subjects who are diagnosed with Malaria will receive antimalarial treatment according to local/ national standards (e.g., a 3-day treatment course of artemisinin-based combination therapy), during the Screening period, to clear the infection prior to vaccination. (Amended 06 May 2015.)***

Another benefit for the subjects may include the gaining of information about their general health status through the medical evaluations/ assessments associated with this study (physical examination, blood testing [haematology and biochemistry data]). All subjects participating to the Screening Visit of this study will be medically examined including testing for haematological (complete blood count [CBC], including differential count and platelet count) and biochemical (alanine aminotransferase [ALT] and creatinine) parameters. Those subjects with clinically significant disease who are not eligible for study participation will be referred for medical care to local facilities. Those subjects who are eligible and participate in the study will receive medical follow-up during the study.

**1.3.3. Overall Benefit : Risk conclusion**

The investigational ChAd3-EBO-Z vaccine is currently in an early stage of clinical development and no vaccine efficacy has been demonstrated. Measures are taken to minimise the risk to subjects participating in this study.

**2. OBJECTIVES****2.1. Primary objective**

- To assess the safety and reactogenicity of a single IM dose of the ChAd3-EBO-Z vaccine, overall and in children aged 1 to 5, 6 to 12, and 13 to 17 years separately.

Refer to [Section 11.1](#) for the definition of the primary endpoints.

**2.2. Secondary objective**

- To assess the humoral immunogenicity of a single IM dose of the ChAd3-EBO-Z vaccine, in terms of anti-GP EBOV antibody responses, overall and in children aged 1 to 5, 6 to 12, and 13 to 17 years separately.

Refer to [Section 11.2](#) for the definition of the secondary endpoint.

**2.3. Tertiary objectives**

[figure not shown]
- To assess the persistence of the humoral immune response induced by a single IM dose of the ChAd3-EBO-Z vaccine, in terms of anti-GP EBOV antibody responses, overall and in children aged 1 to 5, 6 to 12, and 13 to 17 years separately.
- To assess EBOV specific cell-mediated immunity (CMI) of a single IM dose of the ChAd3-EBO-Z vaccine, overall and in children aged 1 to 5, 6 to 12, and 13 to 17 years separately.
- To assess the pre-existing immunity to the ChAd3 virus vaccine vector prior vaccination, ChAd3-specific immune responses after vaccination and explore its potential impact on Ebola-specific immune responses, overall and in children aged 1 to 5, 6 to 12, and 13 to 17 years separately.
- If deemed necessary, to further characterise the immune response to/ the safety profile of the investigational ChAd3-EBO-Z vaccine.

Refer to [Section 11.3](#) for the definition of the tertiary endpoints.

### 3. STUDY DESIGN OVERVIEW

Protocol waivers or exemptions are not allowed with the exception of immediate safety concerns. Therefore, adherence to the study design requirements, including those specified in the outline of study procedures ([Section 5.5](#)), are essential and required for study conduct.

**Figure 1 Study design overview**

**Rando** = randomisation; **yoa** = years of age; **Scr** = Screening; **D** = Day; **M** = Month; **BS (h/b)** = blood sample for haematology/ biochemistry parameters; **BS (I)** = blood sample for humoral immunity; **BS (CMI)** = blood sample for cell-mediated immunity.

Squares indicate visits to the vaccination centre. Rounded rectangles indicate study contacts (home visit or phone call).

Yellow-coloured visits indicate vaccination visits. At the Day 0 visit, subjects in the Group EBO-Z/ MENACWY-TT receive the investigational ChAd3-EBO-Z vaccine and subjects in Group MENACWY-TT/ EBO-Z receive *Nimenrix*. At the Month 6 visit, subjects in Group EBO-Z/ MENACWY-TT receive *Nimenrix* and subjects in the Group MENACWY-TT/ EBO-Z receive the investigational ChAd3-EBO-Z vaccine.

**Subjects will be followed-up for adverse events (AEs) on a daily basis during the 7-day follow-up period after vaccination (day 0 to 6). During this period, AEs will be recorded on a Diary Card. On those days that no study visit is planned, a home visit will be scheduled.**

† The Screening Visit and the Day 0 visit may take place on the same day (allowed interval 0 - 30 days).

\* Only for subjects in the sub-cohort for CMI.

\*\* IDMC review on all available safety data, which will include the safety data up to 7 days after vaccination at Day 0, from at least 50 children (25 per group) in an age stratum before proceeding to vaccination in the next (younger) age stratum (if applicable).

- **Experimental design:** Phase 2, randomised, observer-blind, controlled, multi-country study with 2 groups and 3 age strata.
- **Duration of the study:** For each subject enrolled it will be approximately 12 months from the Day 0 visit
  - Epoch 001: Primary starting at Screening and ending at the Month 12 visit.
- **Study groups:**
  - **Group EBO-Z/ MENACWY-TT:** approximately 300 children in total; approximately 100 children per age stratum (1 to 5 years, 6 to 12 years, and 13 to 17 years of age).
  - **Group MENACWY-TT/ EBO-Z:** approximately 300 children in total; approximately 100 children per age stratum (1 to 5 years, 6 to 12 years, and 13 to 17 years of age).

**Table 1 Study groups and epochs foreseen in the study**

Study group	Number of subjects	Age	Epochs
			Epoch 001
EBO-Z/ MENACWY-TT	~300	~100 children per age stratum: 13 to 17, 6 to 12, 1 to 5 years	x
MENACWY-TT/ EBO-Z	~300	~100 children per age stratum: 13 to 17, 6 to 12, 1 to 5 years	x

~ = approximately

**Table 2 Treatments foreseen in the study**

Treatment name	Vaccine/Product name	Study Groups	
		EBO-Z/ MENACWY-TT	MENACWY-TT/ EBO-Z
ChAd3-EBO-Z	ChAd3-EBO-Z	x (Day 0)	x (Month 6)
Nimenrix	MenACWY-TT NaCl	x (Month 6)	x (Day 0)

**ChAd3-EBO-Z** = investigational recombinant chimpanzee adenovirus type 3-vectored Ebola virus Zaire (EBOV) vaccine; **NaCl** = sodium chloride

- **Control:** Active control (*Nimenrix*).
- **Vaccination schedule:** All subjects will receive 2 vaccinations, 1 at the Day 0 visit and 1 at the Month 6 visit. All subjects will receive 1 dose of the investigational ChAd3-EBO Z vaccine and 1 dose of *Nimenrix*:
  - Subjects in Group EBO-Z/ MENACWY-TT will receive the investigational ChAd3-EBO-Z vaccine at the Day 0 visit and *Nimenrix* at the Month 6 visit.
  - Subjects in Group MENACWY-TT/ EBO-Z will receive *Nimenrix* at the Day 0 visit and the investigational ChAd3-EBO-Z vaccine at the Month 6 visit.

- **Treatment allocation:** Subjects will be randomised (1:1) at Day 0. In order to ensure equal distribution of the population, enrolment will be stratified by age so that an equal number of children are enrolled in each age stratum (1 to 5 years, 6 to 12 years, and 13 to 17 years of age). In addition, the randomisation will use a minimisation procedure accounting for gender and centre.
- **Staggered vaccination:** Vaccination at Day 0 will be done in a staggered manner, starting with vaccination of the children in the oldest age stratum (13 to 17 years of age). In order to proceed to vaccination of the subjects in the younger age stratum (6 to 12 years of age), possibly with a lower vaccine dose, a favourable outcome of the IDMC review of safety data up to at least 7 days after vaccination from at least 50 subjects (25/ group) in the oldest age stratum needs to be obtained. The same will be done for moving from the 6 to 12 years of age stratum to vaccination of the youngest children (1 to 5 years of age). Refer to [Section 9.10](#) for more information.
- **Blinding:**
  - **Observer-blind** from study start until the interim analysis that will be conducted when safety, reactogenicity and immunogenicity (including at least anti-GP EBOV data at Day 30) data is available from all subjects up to 30 days after vaccination at Day 0 (refer to [Section 11.11.1](#) for more information on this interim analysis).
  - **Single-blind** as of the interim analysis *at Day 30. (Amended 06 May 2015.)*
- **Sampling schedule:**
  - *A blood sample (fingerprick) will be taken at Screening for Malaria RDT. (Amended 06 May 2015.)*
  - Blood samples for **haematology/ biochemistry** assessment will be taken from all subjects at Screening, at the Day 3, Day 6, the Day 30, the Month 6, the Month 6 + 6 days, the Month 6 + 30 days, and the Month 12 visits.
  - Blood samples for **humoral immunity** will be taken from all subjects at the Day 0, the Day 30, the Month 6, the Month 6 + 30 days, and the Month 12 visits.
  - Blood samples for **CMI** will be taken from a sub-cohort of 90 subjects per group (30 children per age stratum per group) at the Day 0, the Day 30, the Month 6, the Month 6 + 30 days, and the Month 12 visits.
- **Type of study:** self-contained.
- **Data collection:** eSource.
- **Safety monitoring:** An IDMC will be appointed to monitor the safety and tolerability of the investigational ChAd3-EBO-Z vaccine. The IDMC will consist of clinical experts and a statistician who are not involved in the conduct of the study. Refer to [Section 9.10](#) for detailed description of the safety monitoring.

## 4. STUDY COHORT

### 4.1. Number of subjects/centres

The target is to enrol approximately 600 eligible children (approximately 300 per group and approximately 200 per age stratum). Refer to [Section 11.4](#) for a detailed description of the criteria used in the estimation of sample size. This study will be conducted in West and Central Africa.

### 4.2. Sub-cohort for cell-mediated immunity

A sub-cohort is defined as a group of subjects for whom specific procedures are planned as compared to other subjects. For each group, the first approximately 30 children enrolled in each age stratum will be part of the sub-cohort for CMI (*i.e.*, approximately 90 children per group and approximately 180 children in total; possibly at selected vaccination centres only). A blood sample for assessment of CMI should be taken from these subjects at certain study visits.

**Table 3 Sub-cohort for cell-mediated immunity**

Sub-cohort name	Description	Estimated number of subjects
Sub-cohort for CMI	A blood sample for assessment of CMI will be taken from these subjects at certain study visits.	~30 subjects per age stratum per group (~90 subject per group and ~180 subjects in total)

~ = approximately; CMI = cell-mediated immunity

A subset is defined as a group of subjects for which additional assays are planned as compared to other subjects. Refer to [Section 5.2.3](#) for the description of the subset for additional humoral immunogenicity assays.

### 4.3. Inclusion criteria for enrolment

Deviations from inclusion criteria are not allowed because they can potentially jeopardise the scientific integrity of the study, regulatory acceptability or subject safety. Therefore, adherence to the criteria as specified in the protocol is essential.

All subjects must satisfy ALL the following criteria at study entry:

- Subject's parent(s)/ legally acceptable representative(s) (LAR[s]) who, in the opinion of the Investigator, can and will comply with the requirements of the protocol (*e.g.*, availability for Diary Card completion, return for follow-up visits, availability for clinical follow-up throughout the study period).
- Written/ thumb printed informed consent obtained from the subject' parent(s)/ LAR(s) prior to performing any study specific procedure. In addition, written/ thumb printed informed assent should be obtained if appropriate (from all subjects aged 13 to 17 years and from younger subjects as per local requirements).
- A male or female child aged 1 to 17 years inclusive at the time of **Screening**.  
(Amended 06 May 2015.)

- ***Subjects with a negative RDT test for Malaria within 30 days prior to randomisation into the study.***

***OR***

***Subjects with a positive RDT test for Malaria who completed antimalarial treatment at least 5 days prior to randomisation into the study.***

***(Amended 06 May 2015.)***

- Healthy subjects as per Investigator judgement, as established by medical history, clinical examination and haematology/ biochemistry laboratory parameters screening before entering into the study.
- Female subjects of non-childbearing potential may be enrolled in the study.
  - Non-childbearing potential is defined as pre-menarche or ovariectomy.

Please refer to the [glossary of terms](#) for the definition of menarche.

- Female subjects of childbearing potential may be enrolled in the study, if the subject:
  - has practiced adequate contraception for 30 days prior to the Day 0 visit, and
  - has a negative pregnancy test at the Day 0 visit, and
  - has agreed to continue adequate contraception until 30 days after the Month 6 visit.

Please refer to the [glossary of terms](#) for the definition of adequate contraception.

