**Evaluable:**

Meeting all eligibility criteria, complying with the procedures defined in the protocol, and, therefore, included in the according-to-protocol (ATP) analysis (see [Sections 6.7.2](#) and [11.5](#) for details on criteria for evaluability).

Investigational vaccine:  (Synonym of Investigational Medicinal Product)	A pharmaceutical form of an active ingredient or placebo being tested or used as a reference in a clinical trial, including a product with a marketing authorisation when used in a way different from the approved form, or when used for an unapproved indication, or when used to gain further information about an approved use.
Menarche:	Menarche is the onset of menses for the first time in a young female and is preceded by several changes associated with puberty including breast development and pubic hair growth. Menarche usually occurs within 1 to 2 years of breast development, thelarche. However, a young female can become pregnant before her first menses. Thus, a conservative definition of non-childbearing potential in a pre-menarcheal female is a young female who has not yet entered puberty as evidenced by lack of breast development (palpable glandular breast tissue).
Protocol amendment:	The International Conference on Harmonisation (ICH) defines a protocol amendment as: 'A written description of a change(s) to or formal clarification of a protocol.' GSK Biologicals further details this to include a change to an approved protocol that affects the safety of subjects, scope of the investigation, study design, or scientific integrity of the study.
Protocol administrative change:	A protocol administrative change addresses changes to only logistical or administrative aspects of the study.
Randomisation:	Process of random attribution of treatment to subjects in order to reduce bias of selection.
Self-contained study:	Study with objectives not linked to the data of another study.
Solicited adverse event:	Adverse events to be recorded as endpoints in the clinical study. The presence/occurrence/intensity of these events is actively solicited from the subject or an observer during a specified post-vaccination follow-up period.
Sub-cohort:	A group of subjects for whom specific study procedures are planned as compared to other subjects.

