**CONFIDENTIAL**

202090 (EBOLA Z CHAD3-004)  
Protocol Amendment 2 Final

Type of contact	Visit	Visit	Visit	Visit	Visit	Contact *	Visit	Visit	Visit	Contact *	Visit
Timepoint	Screening 	Day 0 	Day 3	Day 6	Day 30	Month 3	Month 6	Month 6 + 6 days	Month 6 + 30 days	Month 9	Month 12
Record concomitant medications/ products/ vaccinations 		•	•	•	•	•	•	•	•	•	•
Screening Conclusion	•										
Study Conclusion											•

~ = approximately; **AE** = adverse event; **CMI** = cell-mediated immunity; **CRO** = Contract research organisation; **EVD** = Ebola virus disease; **GSK** = GlaxoSmithKline; **RDT** = *Rapid*

**Diagnostic Test**; **SAE** = serious adverse event

• is used to indicate a study procedure that requires documentation in eSource.

○ is used to indicate a study procedure that does not require automatic transfer of the study data fields from the source database into the study database at the CRO.

\* Home visit by field worker or phone call.

 The Screening visit and the Day 0 visit may take place on the same day (allowed interval 0 to 30 days).

 Refer to [Section 5.6.6](#) for the specific assessments included in the physical examination.

 Only if Visit 1 and Screening take place on a different day.

 Only for women of childbearing potential.

 Only if Visit 1 takes place more than 1 week after the Screening Visit.

 Treatment name allocation with randomisation at Day 0; treatment name allocation without randomisation at Month 6.

 Only for subjects in the sub-cohort for cell-mediated immunity (CMI).

 From Screening to Day 0, only those SAEs that are considered related to study participation or to concurrent use of GlaxoSmithKline (GSK) medication/ vaccine need to be recorded.

 Concomitant medications/ products/ vaccinations as described in [Section 6.7.1](#) and [6.7.2](#) need to be recorded in eSource.

 Only for subjects in the oldest age stratum (13 to 17 year olds) and younger subjects as per local requirements.

 **Subjects diagnosed with Malaria at Screening must receive antimalarial treatment according to local/ national standards (e.g., a 3-day treatment course of artemisinin-based combination therapy), during the Screening period.**

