***(Amended 06 May 2015.)***

### **5.6.6. Physical examination**

Perform a complete physical examination of the subject at the Screening, the Day 0, and the Month 6 visit, including assessment of height, weight, body temperature and resting vital signs: heart rate, respiratory rate after at least 10 minutes of rest, and an assessment of the following systems: head/ neck/ thyroid; eyes/ ears/ nose/ throat (EENT); respiratory; cardiovascular; lymph nodes; abdomen; skin; musculoskeletal; and neurological. Breast, anorectal, and genital examinations will be performed when medically indicated. Collected information needs to be recorded in eSource (height only needs to be recorded at Screening).

***For subjects diagnosed with Malaria at Screening, physical examination should be postponed until at least 5 days after completion of Malaria treatment.***

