### 15.4. LABORATORY EVALUATIONS

Document: CHAD3-004-EBO-Z\_Interim\_Final\_SAP\_v2\_0  
Author: PPD Version Number: 2.0 Version Date: 14JUN2017

Template No: CS\_TP\_BS016 – Revision 3  
Effective Date: 01May2012

Reference: CS\_WI\_BS005

- 

The list of laboratory assessments to be included in the analysis is provided in APPENDIX 5: Laboratory Assessments.

The following listings are planned for presentation based on the Total Randomised Cohort:

- Clinical laboratory results, including change from Baseline and toxicity grading.
- Clinical laboratory results: Platelets, including an indication of subjects with AESIs.
- Malaria rapid diagnosis test (RDT) results.
- Pregnancy test results:
  - o Based on the Total Enrolled Cohort and only includes female subjects with results available.

The following tables are planned for presentation based on the Total Vaccinated Cohort:

- Clinical laboratory results, including change from Baseline:
  - o Descriptive statistics, including the interquartile range.Out of range clinical laboratory results:
  - o Number and percentage (%) of subjects with results above or below the normal range.
  - o Percentage (%) is relative to the number of subjects with result available for the specific test and the relevant time point.
- Toxicity grade shift from Baseline to post-baseline, the table will include the following categories:
  - o Grade 0. o Grade 1. o Grade 2. o Grade 3.
  - o Grade 4.
- Clinical Laboratory Percent Decrease from Baseline to Post-baseline: Platelets ( $10^9/L$ ):
  - o Number and percentage (%) of subjects with decrease in platelets in the derived categories will be summarized.
  - o Decrease in platelets from Baseline will be categorised as follows: Any increase
    - 0 to <10% decrease
    - 10% to <20% decrease
    - $\geq 20\%$  decrease o This table will be repeated for the maximum percent decrease observed between Day 3 and Day 6. o This table will not be repeated as a pooled table.
- Reported pregnancies per most recent vaccination and centre:
  - o The number and percentage (%) of reported pregnancies will be presented per most recent vaccination (Day 0 or Month 6) and centre as well as overall.
  - o The percentage will be based on the number of female subjects of childbearing potential within each centre.

All laboratory tables (unless otherwise noted) will be repeated for the following pooling of results:

---

Document: CHAD3-004-EBO-Z\_Interim\_Final\_SAP\_v2\_0

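### Protocol Section 4.3 and the glossary it points to define non-childbearing potential differently for girls before menarche, so some girls could be vaccinated without a pregnancy test being triggered

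*Protocol*

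**What the plan says.** **Eligibility.** Protocol Section 4.3 reads: "Non-childbearing potential is defined as pre-menarche or ovariectomy". It adds no condition on puberty. The line beneath it sends the reader to the glossary "for the definition of menarche".

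**Glossary, entry on menarche.** This entry goes further than defining menarche. It warns: "However, a young female can become pregnant before her first menses". It continues that "a conservative definition of non-childbearing potential in a pre-menarcheal female is a young female who has not yet entered puberty". Puberty is judged there by whether glandular tissue can be felt in the breast. The entry also says that menarche usually follows breast development within 1 to 2 years.

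**Examination.** Section 5.6.6 requires a complete physical examination at Screening, Day 0 and Month 6, but "Breast, anorectal, and genital examinations will be performed when medically indicated".

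**Data capture.** In both SAP versions, Section 10 lists three answers for childbearing potential: yes; no because of hysterectomy, bilateral ovariectomy or tubal ligation; and no because of pre-menarche. The last carries no breast-development condition. Hysterectomy and tubal ligation do not appear in Section 4.3.

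**What depends on the class.** Footnote 4 to protocol Table 5 limits the scheduled pregnancy tests: "Only for women of childbearing potential". Section 5.6.7 has the same limit for testing before vaccination, and so does Section 5.6.2 for the test after a positive malaria rapid test. The contraception criteria in Section 4.3 apply to the same class.

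**Analysis.** SAP version 2.0, Section 15.4, adds a table of reported pregnancies by most recent vaccination and centre: "The percentage will be based on the number of female subjects of childbearing potential within each centre".

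**The concern.** A single yes/no classification decides who is tested for pregnancy, and the protocol defines it in two ways that disagree for one identifiable group: girls with breast development who have not yet had a first menses. The disagreement is in current text, and Section 4.3 itself says that departures from the criteria are not allowed.

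Pregnancy is an exclusion (Section 4.4) and an absolute contraindication at Month 6 (Section 6.6). For a girl classed as non-childbearing, no scheduled procedure looks for it. In Section 5.6.2 the pregnancy result also bears on which antimalarial is proposed. Section 9.10 notes that the vaccine had not yet been given to children. Two sites could class the same girl differently and both believe that they had followed the protocol.

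The same classification feeds the SAP pregnancy table. A pregnancy in a girl recorded as pre-menarcheal would count in the numerator while she is absent from the denominator.

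**Working it through.** **Step 1: the definitions side by side, for a pre-menarcheal girl with breast development**

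| Source | Class | Pregnancy test triggered? |
|---|---|---|
| Protocol 4.3, read alone | Non-childbearing | No |
| eSource category (SAP Section 10) | Non-childbearing | No |
| Glossary, conservative definition | Not non-childbearing | Yes |

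Section 5.6.6 does not make the sign that separates these rows a routine finding. The form offers no way to record it as part of the classification. Both facts favour the first two rows in practice.

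**Step 2: how many girls this concerns**

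Inputs from the documents:
- Protocol Table 4 has six cells of 100: 6 × 100 = 600, which agrees with the stated total. Each stratum has 2 × 100 = 200.
- The 6 to 12 stratum covers 7 single years of age, and the 13 to 17 stratum covers 5.
- The glossary's interval from breast development to menarche is 1 to 2 years.

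Assumptions that the documents do not give:
- Half of each stratum are girls. Minimisation on gender balances the two groups; it does not fix the sex ratio.
- Age is uniform within each stratum.

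Girls classed differently = (200 × share of girls ÷ years of age in the stratum) × interval in years.

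Girls per year of age at a 50% share:
- 6 to 12 years: 100 ÷ 7 = 14.3
- 13 to 17 years: 100 ÷ 5 = 20

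| Interval | All within 6–12 | Half on each side of age 13 | All within 13–17 |
|---|---|---|---|
| 1 year | 14.3 | 17.1 | 20.0 |
| 2 years | 28.6 | 34.3 | 40.0 |

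The range is about 14 to 40.

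Varying the share of girls:
- Lowest corner at 40%: 80 ÷ 7 × 1 = 11.4
- Highest corner at 60%: 120 ÷ 5 × 2 = 48

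The wider range is about 11 to 48.

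**Step 3: the SAP table**

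Suppose a centre has D girls of childbearing potential and P reported pregnancies, of which k are in girls recorded as pre-menarcheal. The table as written shows P ÷ D, although k of the P girls are not among the D. Any k above zero makes this something other than a proportion. The SAP collects status as a baseline characteristic and does not say which visit's status defines D.

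**The case against.** The strongest reply is that these are not two competing rules. Section 4.3 links to the entry that holds the breast-development text, so a careful site reads both together. The entry also calls its definition conservative, which may be advice rather than a limit. This stands in part: the result is ambiguity, not certain omission. A reader might infer that every pre-menarcheal girl will be vaccinated untested, and the cross-reference does not allow that. It does not remove the problem either, because Section 4.3 cites the glossary only for the meaning of menarche and the form follows the unqualified wording.

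A reader might also infer that girls who reach menarche between Day 0 and Month 6 go untested. The documents do not support this. Table 5 schedules a Month 6 test, Section 5.6.7 requires one before any vaccination for females of childbearing potential, and contraindications are checked at each vaccination visit. Such a girl is no longer pre-menarcheal under either definition.

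Nor does it follow that the affected girls would lack contraception. The glossary accepts abstinence as adequate when it is the preferred and usual lifestyle. For many of them the readings differ mainly in the test.

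Breast examination is not forbidden; an investigator who wants the finding may obtain it. The SAP effect needs a pregnancy in a girl still recorded as pre-menarcheal, in a purely descriptive table, and the eSource completion instructions are not available here. These points limit the size of the concern. They do not align the wording.

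**Conclusion.** The concern holds as an unresolved conflict of definition in a rule that controls a safety check. Sites could class a pre-menarcheal girl with breast development either way. Under the reading that Section 4.3 and the form favour, no pregnancy test is triggered for her.

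The count of about 14 to 40 girls is an order of magnitude. Its top end needs a two-year interval lying wholly within ages 13 to 17. The glossary's interval is only what usually happens, so shorter ones are possible. A reader might take the figure as a number of pregnancies or of girls harmed. It is neither: it counts girls whose class depends on which definition a site applies.

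The SAP mismatch is real in the wording but would show only if such a pregnancy were reported.

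**What to change.** 1. **Protocol and eSource.** Reconcile Section 4.3, the glossary entry on menarche, Section 5.6.6, Section 5.6.7, Table 5 footnote 4 and the reproductive-status categories into one operational definition, worded the same in each place. Section 5.6.2 then follows it. Settle in the same step whether hysterectomy and tubal ligation belong in the definition. Which definition applies, and what contraception requirement goes with it, is for the sponsor and investigators.
2. **Timing.** State the visits at which childbearing status is assessed and recorded.
3. **SAP version 2.0, Section 15.4.** State which recorded status defines the denominator, and make sure that no girl with a reported pregnancy is left out because her baseline entry was pre-menarche. One way is to add a percentage based on all vaccinated girls in the centre. Adding only the girls who became pregnant would choose the denominator by outcome.

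The cost is protocol and form wording, possibly one repeated status entry, possibly some further pregnancy tests of a kind that the trial already performs (depending on the definition kept), and one table denominator.
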